- a. Physical risks to the subjects Yes No
- b. Social Risks Yes No
- c. Psychological risks to subjects Yes No
- d. Discomfort to subjects Yes No
- e. Invasion of the body Yes No
- f. Invasion of privacy Yes No
- g. Disclosure of information damaging to subject or others Yes No

3. Does the study involve?

- a. Use of records (Hospital, medical, Death, birth or other) Yes No
- b. Use of foetal tissue or abortus Yes No
- c. Use of organs or body fluids Yes No

4. Are subjects clearly informed about?

- a. Nature and purposes of study Yes No

- b. Procedures to be followed including alternatives used N/A
- c. Physical risks N/A
- d. Private questions Yes No
- e. Invasion of the body N/A
- f. Benefits to be derived Yes No
- g. Right to refuse to participate or to withdraw from study Yes No
- h. Confidential handling of data Yes No
- i. Compensation where there are risks or loss of working time or privacy is involved in any particular procedure Yes No

5. Will signed consent form/verbal consent be required?

- a. From subjects Yes No
- b. From parent or guardian (if subjects are minors) Yes No

6. Will precautions be taken to protect anonymity of subject? Yes No

RESEARCH PROTOCOL

- **Project Title:** A Study on Artificial Intelligence Algorithms for Breast Cancer Classification from Histopathology Images
- **Summary:** Breast cancer, a widespread and potentially fatal illness, emphasizes the urgent requirement for early and precise detection to enhance patient outcomes. The current diagnostic framework, characterized by manual histopathological examination, exhibits inherent drawbacks such as subjectivity and limited throughput. In response, our research aims to transform breast cancer diagnostics by leveraging advanced computational techniques, particularly deep learning. Breast cancer can be classified into two main subtypes: invasive and noninvasive.

Noninvasive breast cancer, often termed *in situ* breast cancer, is characterized by abnormal cells confined within the milk ducts (ductal carcinoma *in situ* or DCIS) or lobules (lobular carcinoma *in situ* or LCIS) without invading surrounding tissues. This type is considered an early stage and typically not life-threatening on its own. Invasive breast cancers are those that spread from the original site (either the milk ducts or the lobules) into the surrounding breast tissue. These constitute approximately 70% of all breast cancer cases and generally have a poorer prognosis compared to the *in-situ* subtypes. [1]

Medical imaging of breasts can be acquired through various techniques, such as MRI scans, mammography, ultrasound, thermography, computed tomography scans, and histopathology. Among these approaches, the histopathology test serves as the gold standard for the clinical diagnosis of cancer. [2]

The proposed AI model aims to streamline and enhance the analysis of histopathological images for the classification of invasive and noninvasive breast cancer, surpassing conventional methods and providing a reliable means of identifying cancerous regions. This promises to significantly improve the accuracy and efficiency of breast cancer diagnostics, meeting the urgent need for dependable and scalable solutions. By automating the complex process of breast cancer histopathological image analysis, our goal is to democratize screening, making it more accessible and reaching underserved populations. Moreover, our model goes beyond technological innovation; it addresses broader issues of accessibility and scalability, particularly in low-income settings. The research's focus on domain adaptation is crucial, ensuring the model's accuracy and reliability across various health facilities. This involves accommodating differences in resources, equipment, and demographic factors, making it a versatile and adaptable solution for diverse contexts.

In summary, our research not only aims to advance the technological frontier in breast cancer diagnostics but also seeks to drive a transformative change in accessibility,

efficiency, and reliability. By developing an AI model that tackles the specific challenges of traditional methods, we aim to make a meaningful impact on breast cancer screening, ultimately leading to early detection, tailored treatment, and improved outcomes for patients worldwide.

- **Introduction:** Breast cancer is a condition where abnormal breast cells proliferate uncontrollably, leading to the formation of tumors. If left untreated, these tumors can metastasize, spreading to other parts of the body and potentially becoming fatal. Breast cancer originates within the milk ducts or lobules of the breast. The initial form, known as *in situ*, is non-life-threatening. However, cancer cells can infiltrate nearby breast tissue, resulting in the development of tumors that manifest as lumps or thickening. Invasive breast cancers have the potential to metastasize to nearby lymph nodes or other organs, posing a significant risk of fatality.

Breast cancer comprises 12.5% of all new cancer cases annually worldwide, rendering it the most prevalent cancer globally. In 2020 alone, 2.3 million women received a breast cancer diagnosis, with approximately 685,000 succumbing to the disease, solidifying its status as the most common cancer. By the close of 2020, 7.8 million women had survived a breast cancer diagnosis within the previous five years, establishing it as the world's foremost prevalent cancer. Breast cancer afflicts women in every nation post-puberty, with incidence rates escalating in later stages of life. [3]

Breast cancer detection typically involves palpation, followed by non-invasive mammogram-based identification of critical points. For confirmation and comprehensive disease profiling, invasive microscopic examination of biopsy samples extracted from the breast's critical mass is conducted. [4]

Early and precise detection of breast cancer is paramount in reducing mortality rates, significantly improving the prognosis and elevating patient survival rates up to 50%. Treatment approaches vary depending on individual factors, cancer type, and extent of spread, often combining surgical intervention, radiation therapy, and medication. In histopathology, the standard procedure for diagnosing breast cancer involves examining a hematoxylin and eosin (H&E) stained tissue biopsy under a microscope. However, this method relies on manual, qualitative inspection, leading to potential investigator bias and low throughput. [5]

Manual examination of histopathological images is labor-intensive and taxing. Moreover, there's a significant risk of overlooking small cancerous regions on slides, especially as malignant cells may be sparsely distributed. In this scenario, machine learning-based automated inspection techniques offer rapid and dependable identification of invasive and noninvasive cancerous cells and regions on the slide. [5] Diagnoses heavily depend on the expertise of medical professionals, introducing subjectivity and limited repeatability, with documented inaccuracies even among experienced practitioners.

Traditional vision screening of histopathological images via light microscopy poses risks of misdiagnosis and struggles with accessibility due to time and personnel limitations. The primary focus is on leveraging advanced computational techniques to automate analysis, addressing inherent drawbacks in traditional screening methods. Through AI approaches, our aim is to create a model surpassing the accuracy of visual assessments, providing a reliable and efficient means of identifying transformation zones and detecting early signs of breast abnormalities. Central to our objective is the recognition of the need for scalable and cost-effective solutions, particularly in low-income settings. The proposed AI model seeks to mitigate the shortage of trained personnel by automating breast cancer histopathological image analysis, streamlining screening and enhancing accessibility. Moreover, we aim to incorporate domain adaptation techniques to ensure the model's precision and resilience across diverse health facilities, considering challenges such as resource constraints, equipment variations, and demographic diversity.

- **Objectives:** Our primary goal is to compile a diverse dataset of breast tissue histopathology images, incorporating samples from various sources to ensure representation across patient demographics and imaging equipment. Using this dataset, we aim to develop a robust AI model for automated classification of invasive and noninvasive breast cancer within histopathology images. Specific objectives include:
 - a) Clinical Validation: Evaluate the AI model's performance through comprehensive clinical validation, measuring sensitivity, specificity, and accuracy in classifying invasive and noninvasive breast cancer types in histopathology images.
 - b) Usability Assessment: Assess the model's usability by involving healthcare professionals in the evaluation process, measuring integration into clinical workflows, result interpretability, and time efficiency during histopathology examinations.
 - c) Impact on Early Detection: Investigate the AI model's impact on early breast cancer detection, analyzing its contribution to identifying cancer types at earlier stages for potentially improved patient outcomes.
 - d) Generalizability: Evaluate the model's generalizability across diverse datasets, including local sources, assessing its performance in different regions and healthcare settings for broader clinical applicability.
 - e) Impact on Patient Outcomes: Examine the AI model's impact on patient outcomes, such as reduced diagnosis time, increased accuracy in cancer type identification, and enhanced treatment planning, considering potential benefits to patient well-being and satisfaction.
 - f) Clinical Decision Support: Evaluate the model's effectiveness as a clinical decision support tool, measuring its contribution to accurate diagnoses and treatment plans during histopathology examinations.

Through these objectives, our research aims to advance breast cancer diagnosis, providing a comprehensive solution that integrates seamlessly with clinical practices and positively influences patient outcomes.

- **Rationale:** Histopathology images contain valuable information about tissue structure, but manual interpretation can be subjective and time-intensive. Deep learning offers a promising solution by automatically learning complex patterns, potentially improving the accuracy and efficiency of breast cancer classification. This research aims to leverage deep neural networks to analyze extensive datasets of histopathology images, distinguishing between invasive and noninvasive breast cancer with high accuracy. Automating this classification process aims to reduce human error, expedite diagnoses, and support personalized treatment approaches. Ultimately, the goal is to refine breast cancer diagnosis, enabling earlier intervention and better patient outcomes.
- **Methodology:** In the clinic-based approach for histopathological breast cancer screening data collection, patient information will be directly gathered within healthcare facilities to develop an AI algorithm for automated cancer detection. This involves capturing essential metadata and clinical details, including histopathological breast images. Utilizing clinic resources, the collected data will train the AI algorithm, offering insights into abnormal findings likelihood during screening. Notably, privacy is prioritized, excluding personally identifiable information in the data collection process.
 - a) **Study Population:** This investigation comprises a prospective and retrospective case-control study designed to develop and assess an AI-based diagnostic tool for breast cancer detection through visual examination. The patient cohorts will include confirmed breast cancer cases diagnosed via gold standard tests and individuals with breast abnormalities resembling cancer (such as Adenosis, Duct Ectasia, Ductal or Lobular Hyperplasia, Fibroadenomas, Fibrosis, Mastitis, Simple Cysts, or other precancerous lesions), along with corresponding confirmatory test results. Additionally, data from individuals with suspected breast cancer (test status unknown) or normal breast condition will be included to support unsupervised learning. The primary aim is to assess the algorithm's ability to differentiate between these patient categories through analysis of their medical image data.

- **Inclusion criteria:**

- Female patients of age 18 years or older can be selected as subjects.
- Individuals willing to participate in breast cancer screening.
- Availability for biopsy examination.
- Women with no current or prior diagnosis of breast cancer.
- Availability of relevant medical records for confirmation and comparison purposes.

▪ **Exclusion criteria:**

- Pregnant women are excluded due to potential impacts on screening results and the necessity for special considerations during pregnancy.
- Individuals with severe medical conditions or circumstances that may render histopathologic examination inappropriate or unsafe are excluded.
- Patients with conditions that could interfere with the accuracy of screening results are excluded.
- Follow-up screenings are not included in this study.

b) **Sample size calculation:** Following the methodology of sample size calculation to evaluate diagnostic performance (for algorithms in this case), we use the following method of calculation for a target sensitivity and specificity incorporating disease prevalence [7]:

$$N_{sen} \geq \frac{Z^2(1-\alpha)/2 \times sen(1 - sen)}{c^2 \times p}$$

$$N_{spec} \geq \frac{Z^2(1-\alpha)/2 \times spec(1 - spec)}{c^2 \times (1 - p)}$$

N_{sen} = Required sample size for sensitivity, sen
 N_{spec} = Required sample size for specificity, $spec$
 α = Confidence level
 $Z^2(1-\alpha)/2$ = The Z-score for the confidence level α
 p = Prevalence of breast cancer
 c = Confidence interval
 sen = Estimated sensitivity
 $spec$ = Estimated specificity

- The final sample size N is calculated based on the larger of the two values N_{sen} and N_{spec} . In this study, as we are using deep learning techniques, we need the medical image samples to reflect the various cancerous, precancerous and normal cases. For our analysis, we assume an 80% confidence level ($\alpha = 0.80$) and prevalence of breast cancer for self-reported instances, $p = 0.261$ [23]. A confidence interval of 5% is selected ($c = 0.05$). We estimate the sensitivity and specificity of our algorithms to be at 75% ($sen = 0.75$ and $spec = 0.75$). Using these values, we obtain the sample size values: $N_{sen} = 471$ and $N_{spec} = 166$. Since $N_{sen} > N_{spec}$, the final sample size for the study will be:

$$N = N_{sen} = 471$$

We can set a target of $N = 500$.

c) Procedures: During the prospective phase of the study, data collection will occur in clinical settings. Eligible patients will be approached during clinic visits and presented with a consent form for their review. Upon agreement, each participant will be assigned a unique identifier to maintain data integrity and ensure patient anonymity. Subsequently, patients will provide essential clinical information. Healthcare professionals will conduct histopathological examinations, and specialized equipment available in the clinic will be used to capture images of the breast region. This method guarantees the collection of non-identifiable data, unique data identifiers, and informed consent directly within the clinical setting, meeting the specific requirements of histopathological breast cancer screening.

In the retrospective phase of the study, additional data will be retrieved from the clinic's database of prior screenings. Due to the retrospective nature, obtaining consent from individual patients is impractical. To address privacy concerns, any personally identifiable patient information will be systematically excluded from the collected data. This ensures compliance with privacy standards while leveraging valuable information from past screenings. While informed consent cannot be obtained for this dataset, the study will strictly adhere to ethical guidelines and prioritize patient privacy during the data extraction process from the clinic's database.

d) Methods of Data Collection:

- Patient ID (unique identification number)
- Date & Time of data input
- Age
- Histopathological breast image data
- Region of Interest (ROI) Annotations:
 - Lesion size
 - Provisional diagnosis
 - Suggested management (e.g., routine screening, biopsy, etc.)
 - Patient's relevant medical/surgical history
- Additional Information (if available):
 - Relevant diagnostic test results
 - Reproductive history

The hematoxylin and eosin (H&E) stained images obtained from histopathological assessment, along with relevant metadata, will significantly contribute to algorithm design and image analysis. These

images' standard test status and corresponding results will serve as the ground truth for our detection algorithm.

e) **Data Interpretation:** Following the completion of data collection, exploratory data analysis will be conducted to assess patient distribution across various parameters, including transformation zone type, histopathology, and relevant clinical factors. Subsequently, a balanced dataset will be curated to ensure fair representation of image samples.

This curated dataset will serve as the foundation for training and evaluating the artificial intelligence (AI) algorithm developed for automatic classification and detection of abnormalities in histopathological breast screening cases. The trained model will generate predictions regarding the presence or absence of abnormalities in the breast images.

To validate the accuracy and clinical relevance of the algorithm's predictions, the results will undergo verification and analysis in collaboration with expert histopathologists. Their insights will be invaluable in refining the automatic algorithm, thereby improving its precision in classifying and detecting potential abnormalities during histopathological breast screenings.

f) **Statistical Analysis:** Once the dataset becomes available, statistical analysis will center on evaluating the performance of the developed artificial intelligence algorithms for automatic classification and detection of abnormalities in histopathological breast screening cases. Key metrics such as sensitivity, specificity, precision, recall, F-1 score, and overall accuracy will be utilized for rigorous evaluation. To ensure robustness, experiments involving n-fold cross-validation will be performed, with mean values and standard deviations of performance metrics calculated. This analysis will conclude with a comparative assessment of various deep learning models, assessing their effectiveness in the automatic classification task.

Utilization of Results: The study results will be pivotal in the development and assessment of an automatic detection algorithm for breast cancer screening, with the following primary objectives:

- a) **Automatic Detection:** Evaluate and detect potential abnormalities in histopathological images, furnishing an automated screening tool for efficient identification of breast cancer risk.
- b) **Clinical Decision Support:** Aid healthcare professionals by furnishing an automated analysis to assist in prioritizing treatment strategies and making informed clinical decisions based on the algorithm's findings.

c) Systematic Data Storage: Enable systematic storage of histopathological images and pertinent metadata to bolster ongoing research efforts, all while safeguarding individuals' privacy during the automated detection process.

These outcomes are poised to significantly enhance the efficiency and accuracy of breast cancer screening, offering valuable support to healthcare professionals in Bangladesh.

- **Facilities:** In the case of collecting data from histopathological breast cancer screening, no additional facilities are required except those the clinics are already equipped with (e.g. image acquisition and data storage capacity).
- **Approval / Forwarding of the Head of Department / Institute / IRB.** A forwarding letter from the Department of Biomedical Engineering, Bangladesh University of Engineering and Technology (BUET) is attached.
- **Flow Chart:** The data collection activity and the corresponding timeline is described in the Gantt chart below:

No.	Work/Activities	Months					
		1	2	3	4	5	6
1	Initial algorithm with publicly available data	■					
2	Collection of images and metadata		■	■	■	■	
3	Homogenization and organisation of data			■	■	■	
4	Data processing and analysis					■	■

- **Ethical Implications:** The proposed retrospective/prospective case-control study based on medical records is designed to develop and evaluate the diagnostic performance of Artificial Intelligence (AI) algorithms that will detect breast cancer stage from histopathological images. The study poses minimal risk to the subjects according to the HHS (USA) definition.
- **References:**
 1. Cruz-Roa, Á., Gilmore, H., Basavanhally, A., Feldman, M. D., Ganesan, S., Shih, N., Tomaszewski, J. E., González, F. A., & Madabhushi, A. (2017). Accurate and reproducible invasive breast cancer detection in whole-slide images: A Deep Learning approach for quantifying tumor extent. *Scientific Reports*, 7(1). <https://doi.org/10.1038/srep46450>

3. World Health Organization: WHO & World Health Organization: WHO. (2023, July 12). *Breast cancer*. <https://www.who.int/news-room/fact-sheets/detail/breast-cancer>

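### Every metric named for the concluding model comparison depends on the decision cut-off, and nothing puts the models at a common operating point, so a cut-off difference can be read as a difference in diagnostic ability

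*Protocol*

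**What the plan says.** The comparison is set out in Methodology f) Statistical Analysis. It names the measures: "Key metrics such as sensitivity, specificity, precision, recall, F-1 score, and overall accuracy will be utilized for rigorous evaluation". It gives the resampling and summary: "experiments involving n-fold cross-validation will be performed, with mean values and standard deviations of performance metrics calculated". It then closes: "This analysis will conclude with a comparative assessment of various deep learning models, assessing their effectiveness in the automatic classification task". No metric is named as the one on which models are ranked.

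Three other places bear on it:

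- Objectives, a) Clinical Validation evaluates the AI model by "measuring sensitivity, specificity, and accuracy in classifying invasive and noninvasive breast cancer types in histopathology images". This concerns validation of one tool, not comparison of several.
- Methodology e) Data Interpretation describes the scored output: "The trained model will generate predictions regarding the presence or absence of abnormalities in the breast images". It also says that "a balanced dataset will be curated to ensure fair representation of image samples".
- Methodology b) Sample size calculation assumes 75% sensitivity and 75% specificity, a prevalence of 0.261, an 80% confidence level and a precision of 0.05.

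The protocol mentions no ROC curve, AUC, precision-recall curve, common sensitivity or specificity, or rule for choosing a cut-off.

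**The concern.** A classifier's sensitivity and specificity reflect two things: how well its scores separate the classes, and where the cut-off is placed. Accuracy, precision and F-1 follow from those two figures and the class mix, so they inherit both influences. Recall adds nothing, being sensitivity under a second name.

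When one tool with a fixed decision rule is validated, this does no harm, because the cut-off is part of the tool. When several networks are compared, it matters. If their cut-offs fall at different points on their ROC curves, two networks with identical curves will show different metrics, and a network that separates the classes less well can lead on a metric that its cut-off happens to favour. Methodology a) gives the primary aim as assessing how well the algorithm tells patient categories apart. That is a question of discrimination, and no named metric isolates it. At stake is whether the study's closing comparison shows which model classifies better or only which one calls more, or fewer, images positive.

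**Working it through.** **The plan's own figures.** With z = 1.28 (80%, two-sided), s = 0.75, c = 0.05 and p = 0.261:

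- N for sensitivity = z² s(1 − s) / (c² p) = 1.6384 × 0.1875 / (0.0025 × 0.261) = 470.8, printed as 471.
- N for specificity = 1.6384 × 0.1875 / (0.0025 × 0.739) = 166.3, printed as 166.

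The figures reproduce. They rest on sensitivity and specificity and are unaffected by this point.

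**Model for the check (an assumption).** Scores are N(0, 1) in negatives and N(d, 1) in positives, with cut-off t. Then sensitivity = 1 − Φ(t − d), specificity = Φ(t) and AUC = Φ(d/√2). From the protocol come 75%/75%, the prevalence of 0.261 and the balanced dataset (taken as 50:50). The other values of d and all shifts in t are illustrative.

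**Step 1: one model, cut-off moved.** 75%/75% requires d = 2 × 0.6745 = 1.349 with t = 0.6745, so AUC = Φ(1.349/√2) = 0.830.

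| Cut-off shift | Sensitivity | Specificity | AUC |
|---|---|---|---|
| −0.4 SD | 0.859 | 0.608 | 0.830 |
| 0 | 0.750 | 0.750 | 0.830 |
| +0.4 SD | 0.608 | 0.859 | 0.830 |

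Sensitivity spans 0.859 − 0.608 = 0.251 with no change in discrimination. Accuracy moves too: at prevalence 0.261, setting specificity to 0.60, 0.75 and 0.90 gives accuracy 0.669, 0.750 and 0.803.

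**Step 2: two models at different cut-offs.** The better model has d = 1.349 (AUC 0.830) and its cut-off 0.3 SD above its symmetric point. The weaker has d = 1.20 (AUC 0.802) and its cut-off 0.3 SD below. With class mix π, F1 = 2π·Se / (π·Se + (1 − π)(1 − Sp) + π).

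| Measure | Better (AUC 0.830) | Weaker (AUC 0.802) | Leader |
|---|---|---|---|
| Sensitivity | 0.646 | 0.816 | weaker |
| Specificity | 0.835 | 0.618 | better |
| Accuracy, 50:50 | 0.741 | 0.717 | better |
| Precision, 50:50 | 0.797 | 0.681 | better |
| F1, 50:50 | 0.713 | 0.742 | weaker |
| F1, prevalence 0.261 | 0.611 | 0.563 | better |

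The weaker model leads on sensitivity and balanced-data F1 only. At prevalence 0.261 the F1 reversal disappears.

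**Step 3: is that pattern general?** Take a better model with d = 1.549 (AUC 0.863) against the 0.830 model.

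- Prevalence 0.261, better at 0.781/0.781 and weaker at 0.461/0.926: the weaker leads on accuracy (0.805 against 0.781), specificity and precision (0.687 against 0.557). The better leads on sensitivity and F1 (0.650 against 0.552).
- Balanced, better at 0.520/0.933 and weaker at 0.75/0.75: the weaker leads on accuracy (0.750 against 0.726) and F1 (0.750 against 0.655).
- Balanced, better at 0.708/0.841 and weaker at 0.75/0.75: the better leads on accuracy (0.775 against 0.750) and F1 (0.759 against 0.750).

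Which metrics reverse, if any, depends on the cut-offs and the class mix.

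**Step 4: a common operating point.** For the pair in Step 2, at specificity 0.75 (t = 0.6745), sensitivity is 1 − Φ(0.6745 − 1.349) = 0.750 against 1 − Φ(0.6745 − 1.20) = 0.700. The order agrees with the AUCs, 0.830 against 0.802.

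**The case against.** **The protocol is silent on cut-offs, and the metric list is open.** A reader might infer that models are judged solely on these metrics and that each network keeps its own or a default cut-off. The document supports neither. The list is introduced by words that leave it open, and no section says how cut-offs are set. An analysis plan that is not shown could add an AUC or a cut-off rule. This stands, and it limits the point to what is named. It does not remove the point: Methodology f) itself chooses the measures, the resampling, the summary and the closing comparison, and all the measures it chose depend on the cut-off.

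**The listed metrics expose the trade-off.** A model that gains sensitivity by calling more images positive visibly loses specificity (0.618 against 0.835 in Step 2). This stands in part. But when one model is higher on one measure and lower on the other, the pair alone does not show which discriminates better.

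**Reversal depends on chosen inputs.** This stands. It would be wrong to infer that a worse model will rank first. It would also be wrong to set the 25-point range beside the planned 5-point precision as like with like, since one is an assumed cut-off shift and the other a sampling margin.

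**Sensitivity, specificity and accuracy suit the validation of a tool that returns a call.** This stands. Objective a) and the sample size rest on them, and they should not be demoted.

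**A single AUC needs a binary target and a score.** This stands. Methodology a) speaks of several patient categories, and the remark about "offering insights into abnormal findings likelihood during screening" is general prose, not a specification of the output. The fix must name the target and assumes that the networks yield a score.

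**Conclusion.** The point holds as a cheap improvement to Methodology f). The metrics named for comparing models all depend on the cut-off, one duplicates another, and no common operating point or cut-off-free measure is fixed. A difference in cut-off can therefore be read as a difference in diagnostic ability. Under the binormal assumption, a 0.4 SD move turns 75%/75% into 86%/61% or 61%/86% at an unchanged AUC of 0.830, and a less discriminating model can lead on some metrics. How often that would happen here cannot be judged, because the protocol gives no cut-offs. The metrics in objective a) are not at fault.

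**What to change.** In Methodology f), state the binary target for the comparison, for example invasive versus noninvasive. Base the comparison of models on two measures:

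- the AUC of the held-out predictions, summarised over folds as the plan already intends;
- sensitivity at one common specificity, for example 75%, the value already assumed for the sample size.

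Set each model's cut-off in the training part of each fold and apply it unchanged to the held-out part. Report the specificity actually reached there, since it will not be exactly the target.

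Keep sensitivity, specificity and accuracy at that cut-off as the validation measures of objective a), consistent with the sample size. Report precision and F-1 as description, and drop recall as a separate entry.

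The cost is some wording and a little more analysis of the same model outputs. No further patients or images are needed, and the sample size of 471 (target 500) does not change.

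### Objective (d) promises performance in different regions and healthcare settings, but no test in an unseen setting is specified and the listed data fields do not assure that one could be done

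*Protocol*

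**What the plan says.** **The aim.** Objectives d) of the protocol sets out to evaluate generalizability across diverse datasets, local ones included, by "assessing its performance in different regions and healthcare settings for broader clinical applicability". Facilities and equipment are named elsewhere. The primary goal under Objectives speaks of "incorporating samples from various sources to ensure representation across patient demographics and imaging equipment", and the Introduction states that "we aim to incorporate domain adaptation techniques to ensure the model's precision and resilience across diverse health facilities". The Summary makes the same point about facilities.

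**The method.** Methodology e) has one balanced dataset curated after collection is complete: "This curated dataset will serve as the foundation for training and evaluating the artificial intelligence (AI) algorithm". Methodology f) gives the only validation design: "experiments involving n-fold cross-validation will be performed, with mean values and standard deviations of performance metrics calculated". The Flow Chart has a month-1 item, "Initial algorithm with publicly available data", and gives those data no role as a test.

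**The data.** Methodology c) combines images from consenting prospective patients with images drawn from an existing database. Methodology d) lists patient ID, "Date & Time of data input", age, the image, annotations and history, with test results and reproductive history if available. It lists no facility, region, device, study phase or date of slide or image acquisition.

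**The concern.** Generalizability is a claim about places the model has not learned from. Cross-validation within one dataset answers a different question: how well the model does on further patients from the sources it was trained on. If folds are not grouped by source, each source sits on both sides of the split, and differences in stain, scanner or case mix between settings never count against the model.

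Two things are at stake. First, internal performance could be reported as the answer to objective (d). Second, archived and new images may differ in appearance. If case mix also differs between them, a model could gain accuracy by recognising the source rather than the disease. Without a study-phase label nobody could check whether this had happened.

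**Working it through.** **1. Objective against method**

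| Needed for objective (d) | What the protocol specifies |
|---|---|
| A test set from a setting not used in training | One curated dataset for training and evaluation (Methodology e) |
| A split that respects source | n-fold cross-validation; n and the fold unit are not given (Methodology f) |
| A label for the setting of each image | No facility, device, phase or acquisition date listed (Methodology d) |
| More than one setting | Unclear: a single clinic's database in Methodology c), several hospitals in the consent-waiver justification |
| An external dataset with a test role | Public data for the initial algorithm only (Flow Chart) |

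The expert review in Methodology e) checks and refines predictions from the same algorithm. It is not a test in a new setting.

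**2. What ungrouped folds would do.** Assume random folds, which the protocol does not state. On average a share (n − 1)/n of each source's patients is then in training whenever that source is tested: 4/5 = 80% for n = 5, and 9/10 = 90% for n = 10.

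**3. The protocol's own sample size.** Inputs from Methodology b): sensitivity and specificity 0.75, c = 0.05, p = 0.261, 80% confidence (z = 1.2816).

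- N_sen = 1.2816² × 0.75 × 0.25 / (0.05² × 0.261) = 471.9
- N_spec = 1.2816² × 0.75 × 0.25 / (0.05² × 0.739) = 166.7

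With z = 1.28 the results are 470.8 and 166.3. The stated 471 and 166 are reproduced. They size one pooled estimate, with nothing set aside for precision by setting.

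**4. Precision by source.** Half-width for sensitivity = z × √(0.75 × 0.25 / m), where m is the number of cancers. The target of 500 gives 500 × 0.261 = 130.5 cancers. The protocol does not give the number of facilities, so k equal facilities are assumed:

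| k | Cancers per facility | Half-width, 80% | Half-width, 95% |
|---|---|---|---|
| 1 (pooled) | 130.5 | 4.9 points | 7.4 points |
| 2 | 65.3 | 6.9 | 10.5 |
| 3 | 43.5 | 8.4 | 12.9 |
| 4 | 32.6 | 9.7 | 14.9 |
| 5 | 26.1 | 10.9 | 16.6 |

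With 26 cancers: 1.2816 × √(0.1875/26) = 0.109, and 1.96 × √(0.1875/26) = 0.166.

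**The case against.** **Fold construction belongs in an analysis plan.** The protocol does not say the folds are random, and a statistical analysis plan not shown here might group them by site. This stands as a limit on the wording: a reader might infer that no unseen setting will ever be tested, but the protocol is silent on this and does not say so. It does not remove the point. Grouping by site needs a site label, and the protocol's list does not include one.

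**The list may not be exhaustive.** The protocol refers several times to further metadata without defining them. Prospective patients sign consent and receive an identifier at enrolment, while archive data come from an extraction without consent, so study phase may be recoverable from study records. A reader might infer that the sources cannot be separated afterwards; that goes too far. What can be said is that the listed fields do not assure separation. The waiver justification also has personal identifiers removed at source, so relying on later recovery is unwise.

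**Public data point to a transfer test.** Objective (d) speaks of diverse datasets including local ones, and a public-data algorithm is scheduled before local collection. That is a fair reading of part of objective (d), and the fix uses it. As written, no such test is specified.

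**Confounding by source is speculative.** A reader might infer that cancers will come mainly from the archive, because the inclusion criteria require no current or prior breast cancer diagnosis and the waiver text calls 500 large against monthly recorded cases. The documents do not support this. The criterion is not limited to the prospective phase, and it does not keep out women whose cancer is first found at biopsy. The remark on monthly cases concerns all samples, and an archive supplies cancers and non-cancers alike. No case mix by phase is given, so no size can be put on this bias.

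**Conclusion.** The concern holds in this form. No test in an unseen setting is specified, and the listed fields do not assure that sources could be separated later. Carried out as written, the study would estimate internal performance only and could not answer objective (d). Bias from mixing archived and new images is possible but unquantified, and it could not be checked from the listed fields.

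That conclusion compares objective with method and rests on no numerical assumption. That the data are pooled is itself an inference, from one curated dataset with no split by source described. The half-widths by facility assume equal facilities, the protocol's prevalence of 0.261 and a sensitivity of 75%. They would change if curation to a balanced dataset altered the share of cancers.

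The change should be made before collection starts, when the labels are cheapest to record.

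**What to change.** **Methodology d).** Add four non-identifying fields: facility code, image-acquisition device, study phase (prospective or retrospective), and date of slide or image acquisition.

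**Methodology f).** Keep the pooled n-fold cross-validation for objective (a), since that is the estimate the sample size supports. State that objective (d) is answered in addition by:

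1. testing the public-data algorithm, frozen, on the local images before any local training;
2. leave-one-facility-out validation, if two or more facilities contribute;
3. sensitivity and specificity reported within each study phase, with training on retrospective and testing on prospective images as a secondary analysis.

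**Objectives d).** If only one facility contributes, restrict the objective to transfer from public to local data and drop the claim about regions and healthcare settings.

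**Cost.** Four fields, further analyses and no extra patients. Reported accuracy may be lower than from pooled folds, and estimates by source will be wide: about ±11 points for sensitivity at 80% confidence, or ±17 at 95%, with 26 cancers. The retrospective-to-prospective test will be equally imprecise if the prospective phase yields only about that many cancers, which is why it should be secondary.
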